4.4.3 Secondary Objective #3: Improvement on clinical composite score (CCS)

The secondary objective #3 is to test the hypothesis that aCRT ON increases the proportion of patients that improve on the Clinical Composite Score (CCS) compared to aCRT OFF, at 6 months of follow-up.

Hypothesis

Let $P_T(\text{improved})$ and $P_C(\text{improved})$ denote the expected probability of having improved clinical composite score at 6 months of follow-up post randomization in the aCRT ON and aCRT OFF arm, respectively. The odds ratio (OR) for aCRT treatment is the odds of having improved CCS at 6 months post randomization in the aCRT ON arm against that in the aCRT OFF arm. The corresponding null and alternative hypotheses are:

$$H_0 : OR = 1$$

$$H_A : OR \neq 1$$

Endpoint Definition

Per CIP, the Clinical Composite Score classifies patients according their clinical status at 6 months of follow-up post randomization into categories Improved, Unchanged, and Worsened.¹⁹

- A patient is classified Worsened in case of death, hospitalization for worsening heart failure, worsened NYHA class compared to Baseline (using last observation carried forward), or worsened status on the Global Assessment Score. Also patients that exit the study or cross over because of worsening heart failure are classified Worsened.
- A patient is classified Improved when not Worsened and there is an improvement in NYHA class at 6 months compared to Baseline, or Global Assessment Score.
- Patients that are not Worsened or Improved are Unchanged.

Analysis Method

In the primary analysis, improvement on CCS will be regarded as a dichotomous endpoint with two categories: Improved and Not Improved (i.e. Unchanged and Worsened). The probability of having improved CCS at 6 months post randomization follows a binomial distribution. The impact of aCRT treatment on improvement of CCS will be evaluated using a marginal generalized linear model similar to the following:

```
proc glimmix data=CCS;  
class site rand NYHA;  
model ImprovedCCS = rand NYHA / dist=binomial link=logit;  
random intercept / subject=site;  
run;
```

where RANDOM statement indicates random intercept effect; SUBJECT=site assumes observations within each site are correlated.

Missing Data

This is not applicable because the derivation of CCS ensures non-missing data.

Determination of Patients/Data for Analysis

The analysis follows the ITT principle and includes all the randomized subjects.

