5.6 Blinding

The study will be single-blinded (i.e. subjects are blinded to randomization assignment) to reduce the effect of bias. Every effort must be made to ensure the randomization assignment is not revealed to the subject.

The Data Monitoring Committee (DMC) will regularly review summarized adverse event data to address potential safety issues. The DMC will be unblinded to subject treatment assignments. However; the EAC will be blinded to the treatment designation when reviewing case files, wherever reasonably achievable.

After all study tests and procedures have been completed just prior to subject exit from the study, the subject may be informed (verbally or in written form) of their randomization assignment.

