5.7 Minimization of Bias

Selection of subjects, treatment of subjects, and evaluation of study data are potential sources of bias. Methods incorporated in the study design to minimize potential bias include (but are not limited to):

- Patients will be evaluated at baseline to confirm eligibility for enrollment with defined inclusion/exclusion criteria prior to implant and randomization.
- An ECG Core Laboratory will be used to confirm presence of LBBB and normal AV conduction.
- Subjects will be randomized to ensure comparable treatment groups.
- Subjects will be blinded to their treatment group.
- Subject demographics will be collected at baseline and differences that may affect primary endpoints will be identified.
- To ensure a widespread distribution of data between centers, the maximum number of randomized subjects allowed per center is no more than 200.
- All implanters in the study will be experienced in the implant of CRT devices.
- Data collection requirements and study procedures will be standardized across all centers and geographies.
- All study center personnel and Medtronic personnel will be trained on their respective aspects of the study using standardized training materials. All study clinicians will be trained on and required to follow the CIP.
- Monitoring visits will be conducted for adherence to the CIP and to verify the CRF data against the source data.
- HF events and deaths will be adjudicated by an independent and blinded EAC.
- An independent DMC will review endpoint and other data to monitor the overall integrity of the study.

- The Steering Committee members will not have influence on the HF treatment decisions by center investigators during the trial, except for approval for crossover, as described in Section 5.5.
- The analysis will be intent-to-treat, following pre-defined statistical methods specified in this Clinical Investigation Plan and the Statistical Analysis Plan.
- Registration of the trial on clinicaltrials.gov and the publication plan will ensure that study results will be reported.

In summary, potential sources of bias that may be encountered in this clinical study have been considered and minimized by careful study design.

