6.8 Randomization

Subjects will be assigned to a treatment at random during the randomization visit, which must occur within 7 days after a successful implant. Centers will receive this assignment electronically in the study database from Medtronic upon completion of the randomization case report form.

At the time of the randomization device programming, a device check will be conducted and the default settings will be verified. If subjects are assigned to the aCRT ON group, "Adaptive Bi-V and LV" will be programmed. If subjects are assigned to the aCRT OFF group, the delegated person will ensure that "Nonadaptive CRT" is programmed. Control group subjects will be optimized per physician's discretion. The method of AV and VV optimization in the control group will be collected. Full device interrogation (Interrogate ALL) data will be collected reflecting the final programming, and a copy of the interrogation files must be sent to Medtronic with a copy being maintained at the center in the subject's file.

The following procedures will be completed / data will be collected at the randomization visit:

- Device programming according to assignment
- AV/VV optimization method (control group only, if optimization occurs per standard of care)
- Final device interrogation (Interrogate All)
- Report AEs, System Modifications, Study Deviations, Crossovers, and Healthcare Utilizations (as they occur)

If randomization does not occur within 37 days after enrollment, verification of all inclusion and all exclusion criteria must be repeated before randomization.

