90 Month follow-up	2709	2739	2769

6.9.1 3 and 6 month Follow-up visits

- NYHA HF assessment
- Physical examination
- Blood measurements (if collected per standard of care)
- Current CV medications
- Current heart failure symptoms status
- Final device interrogation (Interrogate All)
- AV/VV optimization method (control group only, if optimization occurs per standard of care)
- Quality of Life and Health Outcome Measures:
 - Kansas City Cardiomyopathy Questionnaire (KCCQ)
 - EQ-5D
- Patient Global Assessment
- Report AEs, System Modifications, Study Deviations, Crossovers, and Healthcare Utilizations (as they occur)

6.9.2 12, 18, 24 month Follow-up visits

- NYHA HF assessment
- Physical examination
- Blood measurements (if collected per standard of care)
- Current CV medications
- Current heart failure symptoms status
- Final device interrogation (Interrogate All)
- AV/VV optimization method (control group only, if optimization occurs per standard of care)
- Quality of Life and Health Outcome Measures
 - Kansas City Cardiomyopathy Questionnaire (KCCQ)
 - EQ-5D
- Report AEs, System Modifications, Study Deviations, Crossovers, and Healthcare Utilizations (as they occur)

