11.5.1 Secondary objectives

To assess all-cause mortality in the aCRT ON arm compared to aCRT OFF.

Mortality will be illustrated with Kaplan-Meier graphs. A Cox proportional hazards regression model will be used to estimate the HR of aCRT compared to control, which will be reported with its p-value and 95% confidence interval. The model will include the stratification variables also included in the primary objective model.

To assess the rate of intervention for heart failure decompensation for aCRT ON compared to aCRT OFF.

Incidence of intervention for heart failure decompensation will be illustrated with cumulative incidence graphs. A Cox regression model will be used to estimate the cause-specific HR of aCRT compared to control, which will be reported with its p-value and 95% confidence interval. The model will include the stratification variables also included in the primary objective model. Additionally, recurrent event survival analysis will be performed to compare rates of interventions for heart failure decompensation.

To test the hypothesis that aCRT ON increases the proportion of patients that improve on the Clinical Composite Score (CCS) compared to aCRT OFF, at 6 months of follow-up.

The Clinical Composite Score classifies patients according their clinical status at 6 months post randomization into categories Improved, Unchanged, and Worsened²². A patient is classified Worsened in case of death, hospitalization for worsening heart failure, worsened NYHA class (using last observation carried forward), or worsened status on the Global Assessment Score. Also patients that exit the study or cross over because of worsening heart failure are classified Worsened. A patient is classified Improved when not Worsened and there is an improvement in NYHA class or Global Assessment Score. Patients that are not Worsened or Improved are Unchanged.

The proportion of patients who Improved will be compared between the arms of the study with a logistic regression model, correcting for the stratification variables also included in the primary objective model.

To test the hypothesis that aCRT reduces the incidence of AF compared to aCRT OFF.

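### The Clinical Composite Score uses NYHA class from sites that hold the assignment, and no blinded rater or blinded-component sensitivity analysis is specified

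*SAP*

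**What the plan says.** **Blinding.** Protocol 5.6: "The study will be single-blinded (i.e. subjects are blinded to randomization assignment) to reduce the effect of bias". Protocol 6.8 adds: "Centers will receive this assignment electronically in the study database from Medtronic upon completion of the randomization case report form". The site then programs the device to that assignment.

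**The visit that yields the score.** Protocol 6.9.1 lists for the 3- and 6-month visits an NYHA assessment, a device interrogation, the "Patient Global Assessment" and a control-only item: "AV/VV optimization method (control group only, if optimization occurs per standard of care)". Neither document names the NYHA rater or says what that person may know.

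**The score.** SAP 4.4.3: "A patient is classified Improved when not Worsened and there is an improvement in NYHA class at 6 months compared to Baseline". The sentence does not end there; the full condition is "an improvement in NYHA class at 6 months compared to Baseline, or Global Assessment Score". Worsened follows from any one of death, hospitalization for worsening heart failure, worsened NYHA class or worsened Global Assessment. Protocol 11.5.1 has the same rule and continues: "Also patients that exit the study or cross over because of worsening heart failure are classified Worsened".

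**Independent assessment.** Protocol 5.7: "HF events and deaths will be adjudicated by an independent and blinded EAC". NYHA class is not covered.

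**Analyses.** SAP 4.4.3 gives one CCS model, a logistic regression on all randomized patients. SAP Table 2 lists only the primary analysis for secondary objectives #3 to #7. Under SAP 4.4, CCS enters the Hommel procedure with six other objectives and is tested at the final stage whatever the primary result.

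**The concern.** Protocol 11.2.1 relies on blinded adjudication to keep the primary comparison fair. The NYHA part of CCS has no such safeguard. It is a graded clinical judgement made at a site that holds the assignment, at a visit where programming is interrogated and one form item applies to controls only. The judgement can create Improved, and through the Worsened rule it can also cancel the blinded patient's own favourable rating. The reason given for an exit or crossover is a second component for which no blinded review is specified.

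With about 3500 patients, a modest net difference between arms is enough for significance. CCS could then be reported as a family-wise-controlled benefit, and no planned analysis would show whether it rested on open ratings.

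**Working it through.** **1. The plan's own figures.** The documents give no power or effect size for CCS, so there is none to reproduce. The alpha available to the secondary family does reproduce. Pocock-type spending, 0.05 × ln(1 + (e − 1)t) at t = 0.25, 0.50, 0.75 and 1, gives 0.0179, 0.0310, 0.0414 and 0.05; SAP 4.4 states 0.018, 0.031, 0.041 and 0.05. With seven tested objectives at the final analysis, the Hommel bar for CCS lies between 0.05/7 = 0.00714 (z = 2.69) and 0.05 (z = 1.96).

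**2. Inputs.** About 3500 patients randomized 1:1 (Protocol 1.2, 5.4) give 1750 per arm. SAP 4.4.3 treats CCS as never missing, so all are analysed. The improved proportion is an assumption, 70%. It lies between the earlier study's control rates in Protocol 2: 68.4% in the subgroup resembling this population and 72.5% overall. The check is a two-proportion comparison that ignores the site and NYHA terms in the model.

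**3. Net difference that reaches significance.**

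SE = √(2 × 0.70 × 0.30 / 1750) = 0.0155, or 1.55 points.

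- At 0.05: 1.96 × 1.55 = 3.0 points.
- At 0.05/7: 2.69 × 1.55 = 4.2 points.

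With control rates of 68.4% and 72.5%, the thresholds are 3.04 and 2.91 points at 0.05 (53 and 51 patients in one arm), and 4.15 and 3.96 points at 0.05/7 (73 and 69 patients).

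**4. Chance of rejection from bias alone.** With no true effect and a net bias d, P = 1 − Φ(z − d/SE).

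| Net bias | d/SE | at 0.05 | at 0.05/7 |
|---|---|---|---|
| 3 points | 1.94 | 49% | 23% |
| 5 points | 3.23 | 90% | 70% |

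Over control rates of 68.4% to 72.5% the ranges are 49–53% and 23–25% at 3 points, and 90–93% and 72–77% at 5 points.

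**5. Which column applies.** I simulated the full Hommel procedure with bias in CCS only and no effect on the other six objectives, at correlations of 0 to 0.5. CCS was rejected in about 23% of trials at 3 points and 70–71% at 5 points. The 0.05/7 column is therefore the one to read if nothing else is positive. The 0.05 column is an upper limit, approached only when the other objectives also have small p-values.

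**6. Net shift against ratings moved.** An over-favourable rating creates Improved only in a patient who is neither Worsened nor already Improved by either route. If 10% to 25% of an arm would otherwise be Unchanged (an assumption; the documents give no figure), the share of those patients to be up-rated is:

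- to reach 0.05: 3.0/25 = 12% to 3.0/10 = 30%;
- to reach 0.05/7: 4.15/25 = 17% to 4.15/10 = 42%.

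This counts one kind of movement only. Patients Worsened by NYHA alone, and controls Improved by NYHA alone, can also move. Opposite shifts in the two arms would halve what each arm needs.

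**The case against.** **CCS does not rest on NYHA alone.** The blinded patient's Global Assessment is a separate route to Improved, and a worsened Global Assessment overrides any NYHA gain. This stands. A reader might infer that the score turns on NYHA; the full sentence in SAP 4.4.3 does not support that.

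**No text says the rater knows the arm.** Protocol 6 lets sponsor personnel program and interrogate devices under site supervision, so the NYHA rater may be someone else. This also stands: the rater's knowledge is a strong inference from Protocol 5.6, 6.8 and 6.9.1, not a stated fact. Leaving it open is part of the gap.

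**The shift is not obviously small.** Three points could be read as about one rating in 33 being wrong. It is a net CCS difference, and the share of decisive ratings that must move is larger. No document gives any size for rater bias.

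**Expectation among raters is speculative.** The earlier study's overall CCS result was 73.6% against 72.5%; the larger gap, 80.7% against 68.4%, came from a post-hoc subgroup. Fair, and the point does not depend on it.

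**Other parts of the plan help.** KCCQ and EQ-5D are completed by blinded subjects and tested in the same family, crossovers normally need Steering Committee approval, and SAP 2 expects further analyses. These help interpretation, but none shows whether a CCS difference survives without NYHA, and an analysis chosen afterwards does not constrain the claim.

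**Conclusion.** The point holds as a vulnerability in a formally tested secondary objective. NYHA class is one of two routes to Improved and sufficient for Worsened, it comes from sites that hold the assignment, and neither a blinded rater nor a blinded-component CCS analysis is specified.

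A net difference of about 3 points would reach p = 0.05, and about 4 points would reach 0.05/7. The fairer rejection figures for bias alone are about 23% at 3 points and 70% at 5 points; 49% and 90% ignore the planned multiplicity control. All rest on 1750 per arm, about 70% improved, no true effect and a simple two-proportion comparison.

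A reader might go further and conclude that CCS will be biased, or that a significant result would be an artefact. The documents support neither. Baseline NYHA precedes randomization and is unaffected, and the primary endpoint is adjudicated separately. The matter is a worthwhile, inexpensive improvement.

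**What to change.** Keep the CCS primary analysis in SAP 4.4.3 as it is. Add there, and in Table 2, one pre-specified sensitivity analysis: the same logistic model on a CCS built from death, EAC-adjudicated HF hospitalization and the subject-rated Global Assessment, leaving out NYHA class and investigator-stated reasons for exit or crossover. Say whether the HF hospitalization in the primary CCS is also the adjudicated one, since 4.4.3 does not. State who rates NYHA and whether that person knows the arm.

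Report the sensitivity estimate and confidence interval beside the primary CCS result, and qualify any CCS benefit that it does not show. I would not make the claim conditional on agreement in direction: with no true effect, the two versions would agree by chance at least half the time, so the condition protects little.

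The cost is one more model on data already collected. The reduced score has fewer components than the standard CCS definition. It is also not perfectly blinded, because Protocol 5.6 blinds the EAC only as far as reasonably achievable. It should therefore stand beside the primary CCS, not replace it.

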4.4.4 Secondary Objective #4: Incidence of atrial fibrillation (AF)

The secondary objective #4 is to test the hypothesis that aCRT ON reduces the incidence of AF compared to aCRT OFF.

Hypothesis

Occurrence of AF will be recorded in device data. The endpoint will be the first day after randomization on which there is >6 hrs of AF reported in the device's Cardiac Compass Trends.

Considering the presence of death as a competing risk, the cumulative incidence function of AF event in the treatment arm, $F_T(t)$, and control arm, $F_C(t)$, are the proportion of patients that have had the first >6 hrs AF episode prior to time t .

In the primary analysis, Cox regression will be used for competing risk analysis where only the hazard of the event of interest is modeled and there is no simple connection between covariate effect from Cox model and cumulative incidence curves.

Let $h_T(t)$ and $h_C(t)$ be the associated hazard functions. Under the Cox regression model, $h_T(t) = HR \cdot h_C(t)$, where HR is the hazard ratio of treatment compared to control for occurrence of the first >6 hrs AF episode. The null and alternative hypotheses can be expressed as:

$$H_0 : HR = 1$$

$$H_A : HR \neq 1$$

Analysis Method

The same methods used for HF event in secondary objective #2 will be used for the AF endpoint here.

The crude cumulative incidence curves of AF endpoint will be displayed by treatment and NYHA class combinations using %CUMINCID:

```
%cumincid(data=AF, time=TtoAF, status=AFcens, event=1, compete=2, censored=0, strata=randNYHA)
```

where TtoAF starts from the date of randomization and ends at the date that the first >6 hrs of AF was reported in the device's Cardiac Compass Trends for those who experienced this event, or the date of death for those who died before experiencing a AF event, or the date of last documented follow-up (including the date of last available device data) for those who are censored. AFcens = 0 when a subject did not experience an AF event or death and therefore was censored; AFcens = 1 when a subject experienced an AF event the first time since randomization; AFcens = 2 when a subject died without experiencing an AF event. The competing risk of AF event exists when AFcens = 2.

In addition, device measured AF burden and treatment for AF will be summarized. Device measured AF burden is defined as the daily time in AF as captured in Cardiac Compass averaged over all days with data. For AF reported as an adverse event, its symptoms and treatment taken documented in the CRFs will be listed.

The hypothesis regarding the aCRT effect on AF will be tested using a Cox proportional hazards regression model with a random site effect (frailty), stratified by NYHA class at enrollment. Section 4.3.2 has described this model in details. The analysis will be conducted using code similar to:

```
PROC PHREG DATA=AF;  
  CLASS NYHA site;  
  MODEL time*AF(0) = rand / TIES=efron;  
  STRATA NYHA;  
  RANDOM site/dist = gamma;  
RUN;
```

In these codes, AF = 1 given the occurrence of >6 hrs AF episode and AF = 0 otherwise; time to AF starts from the date of randomization and ends at the date when the first >6 hrs of AF was reported in the device's Cardiac Compass Trends for those who experienced this event, or the date of last documented follow-up or date of death for those who are censored.

The model assumptions will be checked using the same methods that are described in detail in section 4.3.2 for the primary endpoint. That is, the assumption of proportional hazards between the treatment arms will be checked by testing the significance of treatment by time interaction term; and, the assumption of constant hazard ratio for treatment across NYHA classes will be checked by testing the significance of treatment by NYHA class interaction and evaluating the hazard ratio for treatment within each NYHA class.

Missing Data

Non-informative censoring is assumed for lost to follow up in the analysis of defined AF event.

Secondary Competing Risk Analysis: Fine-Gray Regression

In addition to the Cox regression as the primary analysis for AF, Fine-Gray regression will be conducted as a secondary competing risk analysis.

Let $h_T(t)$ and $h_C(t)$ be the subdistribution hazard of $F_T(t)$ and $F_C(t)$, respectively. Under the Fine-Gray model¹⁴ that assumes proportional subdistribution hazards, $h_T(t) = \text{SHR} \cdot h_C(t)$, where SHR is the subdistribution hazard ratio of treatment compared to control for occurrence of the first >6 hrs AF episode. The null and alternative hypotheses are:

$$H_0 : \text{SHR} = 1$$

$$H_A : \text{SHR} \neq 1$$

The hypothesis regarding the aCRT effect on incidence of the first >6 hrs AF will be tested using a stratified Fine-Gray model:

```
data Risk;
  NYHAc=2; rand=1; output;
  NYHAc=2; rand=0; output;
  NYHAc=3; rand=1; output;
  NYHAc=3; rand=0; output;
  NYHAc=4; rand=1; output;
  NYHAc=4; rand=0; output;
run;
proc phreg data=AF plots(overlay=stratum)=cif ;
  class NYHAc rand;
  model TtoAF*AFcens(0)= rand / eventcode=1;
  strata NYHAc;
  hazardratio 'Pairwise' rand / diff=pairwise;
  baseline covariates=Risk out=out1 cif=_all_ / rowid=rand;
run;
```

Determination of Patients/Data for Analysis

The analysis follows the ITT principle and includes all the randomized subjects.

